### **5.3 Exclusion Criteria**

- Patients aged younger than 18 years old who are undergoing the above eyelid procedures in an office, ambulatory care centers, operating rooms;
- patients undergoing chalazion removal;
- patients who have had previous wound infections at the site of the procedure;
- patients with oral or IV antibiotic use within 10 days prior to procedure;

- patients requiring IV antibiotics during the procedure;
- patients with grossly contaminated or inflamed wounds;
- patients with human or animal bites,
- patients with wounds resulting from trauma
- patients who are allergic to all study drug options.

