	

• entropion repair;

• external dacryocystorhinostomy;

• external levator resection;

• eyelid lesion removal and/or biopsy;

• eyelid reconstruction and defect repair including after Mohs surgery;

• fat pad excision (upper and lower lids);

• gold or platinum weight implantation;

• internal levator resection;

• lateral tarsal strip;

• orbital fracture repair requiring periorbital incisions;

• orbitotomy requiring periorbital incisions;

• tarsorrhaphy;

• wedge excision.

• Patients undergoing repeat procedures will also be included.

 
Exclusion Criteria:
 

• Patients aged younger than 18 years old who are undergoing the above eyelid procedures in an office, ambulatory care centers, operating rooms;

• patients undergoing chalazion removal;

• patients who have had previous wound infections at the site of the procedure;

• patients with oral or IV antibiotic use within 10 days prior to procedure;

• patients requiring IV antibiotics during the procedure;

• patients with grossly contaminated or inflamed wounds;

• patients with human or animal bites,

• patients with wounds resulting from trauma

• patients allergic to all study drug options.

--	--

TEST PRODUCT, DOSE, AND ROUTE OF ADMINISTRATION	Topical Ophthalmic Antibiotic Ointment (e.g. poly-bacitracin, bacitracin). Apply a thin ribbon to surgical wounds 4 times a day (while awake) for 7 days.
CONTROL PRODUCT, DOSE AND ROUTE OF ADMINISTRATION	Artificial Tear Ointment (e.g. Refresh PM). Apply a thin ribbon to surgical wounds 4 times a day (while awake) for 7 days.
DURATION OF SUBJECT PARTICIPATION AND DURATION OF STUDY	Subjects will be on study for up to 14 days. Screening: During pre-operative assessment. Treatment Duration: 7 days Follow-up: 7-14 days The total duration of the study is expected to be 2 years with ongoing subject recruitment. Each subject will have a final follow-up at post-operative week 1 and/or post-operative week 2 unless a post-operative infection occurs. In the event of a post-operative infection, final follow-up will occur upon infection resolution.
CONCOMITANT MEDICATIONS	Allowed: All non-antimicrobial medications.  Prohibited: Antibiotics taken by IV or by mouth.

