## 3 STUDY DESIGN

### 3.1 Study Overview

This is a single center, placebo-controlled, randomized trial. 400 subjects are planned. Subjects will be randomly assigned to a study drug or to a placebo. Each subject will apply a single dose of topical study drug or placebo four times daily to their surgical wounds over the course of one week.

Screening data will be reviewed to determine subject eligibility. Subjects who meet all inclusion criteria and none of the exclusion criteria will be entered into the study.

The following treatment regimens will be used:

- Experimental treatment: topical ophthalmic antibiotic ointment (e.g. erythromycin, bacitracin or polybac)
- Placebo: artificial tear ointment (e.g. Refresh PM)

Total duration of subject participation will be from the time of approval for eyelid surgery to post-operative visit #1 (either one or two weeks after surgery). Total duration of the study is expected to be 2 years.

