#### Control:

Refresh PM Lubricant Eye Gel, 3.5g

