### 7.4.2 Dispensing

Study drug or placebo will be dispensed by an outpatient pharmacist.

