## 7.7 Measures of Treatment Compliance

Subjects will be asked to keep a patient diary noting the day and date they take their study drug and any adverse events. They will be asked to bring their patient diary to each study visit along with all used and unused study drug containers.

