## 9.2 Visit 2 (Post-operative week 1)

1. Record any Adverse Experiences and/or Review subject diary for adverse experiences and dosing compliance.
2. Concomitant medications review.
3. Perform abbreviated eye examination.
4. Determine presence or absence of surgical site infection.
5. Determine presence or absence of drug/placebo allergies.
6. Determine if patient is immunocompromised.
7. Start treatment if infection present.
8. Document findings using Apex smartphase, “.RKRVEYELIDPOST”

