4.2 Secondary outcomes

Frequency of wound complications

Allergic contact dermatitis

Wound dehiscence

Frequency of surgical site infection (superficial and deep incisional) among subgroups (low- versus high-risk patients for infection)

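### The allergy exclusion does not cover known allergy to the single control ointment, and its term for the study products is undefined, so some eligible patients could not take both assignments

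*Protocol*

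**What the plan says.** Protocol section 5.3 excludes "patients who are allergic to all study drug options", and the synopsis has the equivalent "patients allergic to all study drug options". No other criterion mentions allergy.

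Section 7.3 offers three antibiotic ointments as alternatives (erythromycin, bacitracin, and bacitracin with polymyxin B) and one control product, "Refresh PM Lubricant Eye Gel, 3.5g". Section 7.1 allocates 1:1 and states no restriction for allergy.

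The term *study drug* is used in two ways:

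- Section 3.1 separates it from the control: "Subjects will be randomly assigned to a study drug or to a placebo". Section 7.4.2 does the same: "Study drug or placebo will be dispensed by an outpatient pharmacist". Sections 7.4 and 8 follow this usage.
- Section 7.7 appears to use it for whatever ointment the subject was given: "Subjects will be asked to keep a patient diary noting the day and date they take their study drug and any adverse events".

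At Visit 1 (section 9.1) the history step names antibiotic use but not allergy, and randomization follows. Allergy is first named at Visit 2, after treatment: "Determine presence or absence of drug/placebo allergies". In SAP section 4.2, "Allergic contact dermatitis" is listed under the secondary outcome of wound complications. SAP section 6.2 compares the arms on it by Fisher's exact test, with a risk ratio and 95% confidence interval.

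**The concern.** In a two-arm trial, every randomized patient should be able to take either assignment. An allergy criterion serves that aim only if it is checked arm by arm. This one is a single condition, joined by the word *all*, over a set of products that the protocol does not define.

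Two things are at stake. The first is safety: the rule as written lets a patient be assigned to an arm whose only product is a known allergen for that patient. The second is the dermatitis outcome. Contact dermatitis from antibiotics is part of the trial's rationale (synopsis; section 1), and section 4.2 counts complications of both ointments. Foreseeable reactions to the control ointment would work against the harm that the trial hopes to measure. If the ointment is not used instead, adherence in that arm falls.

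**Working it through.** **Plan's own figure.** The documents give no figure for allergy. The only power statement is SAP 2.1: 87% for infection rates of 0.2% v 5% with about 200 per arm. Exact enumeration of two binomials (n = 200 each) with a two-sided Fisher test at 0.05 gives 87.1%, so it reproduces. Allergy does not enter that calculation.

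**Who is eligible under each reading.**

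| Known allergy | *Study drug* = antibiotics only | *Study drug* = both arms |
|---|---|---|
| One or two antibiotics only | Eligible | Eligible |
| All antibiotics, not control | Excluded | Eligible; 1/2 chance of an arm with no tolerated product |
| Control, not all antibiotics | Eligible; 1/2 chance of the control | Eligible; 1/2 chance of the control |
| Every product in both arms | Excluded | Excluded |

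The third row fails on both readings. The second fails only on the broad one.

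**Which reading is likelier.** Sections 3.1, 7.4, 7.4.2 and 8 contrast the two terms, and a plural set of options fits the three antibiotics better than the single control. That favours the narrow reading, but the text does not settle it. Section 7.7 uses the term broadly. Section 13.1 names both products when it defines the analysis set, then only the study drug when it defines the safety population. The examples of antibiotics also vary: the synopsis treatment row and section 7.4.1 do not name erythromycin, while sections 3.1 and 7.3 do.

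**Illustrative size.** Let *f* be the prevalence of known allergy to the control ointment. The documents do not give it, so 0.5% to 2% is an assumption.

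- Expected allergic patients enrolled: 400 × *f* = 2 to 8.
- Expected in the control arm: 400 × *f* × 1/2 = 200 × *f* = 1 to 4.
- Chance of at least one in that arm: 1 − (1 − *f*)^200 = 63% at 0.5%, 98% at 2%.
- Added dermatitis rate if all use the ointment and all react: 1/200 to 4/200 = 0.5 to 2 percentage points.

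For *k* events against none, with 200 per arm, the two-sided Fisher p is 2 × C(200,*k*)/C(400,*k*):

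| *k* v 0 | p |
|---|---|
| 4 | 0.12 |
| 5 | 0.061 |
| 6 | 0.030 |

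Six expected events would need *f* = 6/200 = 3%, above the assumed range. These are expected counts, and the actual number would vary around them.

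**The case against.** Several safeguards make actual exposure unlikely. Section 5.2 requires that the subject be able to comply with the study, which a patient who cannot use one of the two ointments arguably fails. Section 3.1 has screening data reviewed for eligibility, and medical history is taken before randomization. Nobody is blinded (section 7.2), and a pharmacist dispenses a labelled product. A known allergen would have to get past surgeon, pharmacist and patient, so non-use is likelier than a reaction. All of this stands as a reason to expect few events. It does not repair the criterion, because it relies on judgement at points where the protocol does not ask about allergy.

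A reader might also infer four stronger things, which the documents do not support:

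- *That a patient allergic to everything in either arm can be randomized to it.* On the protocol's usual contrast, a patient allergic to every antibiotic is exactly the one excluded. The gap reaches the antibiotic arm only on the broad reading.
- *That the comparison is confounded.* Randomization gives both arms the same expected share of allergic patients. A difference in dermatitis would be a real effect of the assigned product in the population enrolled. The question is whom to enrol.
- *That patients who avoid the ointment drop out of the analysis.* SAP section 7 omits only those whose outcome is missing. SAP section 5.1 makes all randomized subjects the primary population, replacing the completers' set in Protocol 13.1, and section 13 allows the SAP to make such changes. Protocol 11.1 asks those who stop to keep attending. A non-user who is assessed stays in.
- *That antibiotic allergy is steered around while control allergy is not.* Three alternatives make this possible, but no section says how the product is chosen.

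**Conclusion.** The criterion has a gap. Whichever way *study drug* is read, a patient with a known allergy to the control ointment is eligible unless also allergic to all the antibiotics, and has a 50% chance of assignment to it. If the term covers both arms, the gap extends to patients allergic to all the antibiotics.

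This is a matter of eligibility and safety that touches one component of a secondary outcome. It does not bias the randomized comparison, and the 87% power for infection is unaffected. The effect on dermatitis cannot be sized from the documents. The illustration of 1 to 4 control patients rests on an assumed prevalence of 0.5% to 2%, on every such patient using the ointment and reacting, and on no events in the other arm. At those counts, the reactions alone would not reach p < 0.05. With events this rare they could still shift the risk ratio. The change is worth making because it is specific and cheap.

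**What to change.** - Define *study drug options*, and reconcile the synopsis with sections 3.1, 5.3, 7.3, 7.4.1 and 7.7 on which products the term covers.
- State the allergy exclusion separately for each arm, in section 5.3 and the synopsis, so that every randomized patient could receive either assignment.
- Add known ointment allergy to the history at Visit 1 (section 9.1), before the randomization step.

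The cost is a short wording amendment and the loss of a few recruits (2 to 8 of 400 under the assumed prevalence, for the control ointment).

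The SAP, dated 4/1/2020, describes randomization and outcome assessment partly in the past tense. If enrolment has closed, an amendment can no longer act. What remains is to report by arm, as far as the records allow, how many patients had a known ointment allergy at entry, how many did not use the assigned ointment for that reason, and how many of the dermatitis cases were theirs.

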## 6 CONCURRENT MEDICATIONS

All subjects should be maintained on the same medications throughout the entire study period, as medically feasible, with no introduction of new chronic therapies.

The following medications are prohibited during the study and administration will be considered a protocol violation:

- Intravenous antibiotics.
- Oral antibiotics.

## 7 STUDY TREATMENTS

### 7.1 Method of Assigning Subjects to Treatment Groups

Patients will be randomly assigned to topical antibiotic ointment or placebo treatment groups in a 1:1 ratio using a computer-generated randomization scheme developed by the study statistician. Randomization will be performed at the time of study recruitment.

### 7.2 Blinding

Neither subjects nor investigators will be blinded.

### 7.3 Formulation of Test and Control Products

#### Test:

Erythromycin Ophthalmic Ointment USP, 0.5%, 3.5g, Akorn

OR

Bacitracin Zinc Ophthalmic Ointment USP, 3.5g, Bausch+Lomb

OR

Bacitracin Zinc and Polymyxin B Sulfate Ophthalmic Ointment USP, 3.5g, Bausch +Lomb

#### Control:

Refresh PM Lubricant Eye Gel, 3.5g

#### 7.3.1 Packaging and Labeling

Study drug will be supplied in single 3.5 g tubes and will be labeled per the manufacturer.

## 7.4 Supply of Study Drug at the Site

Study drug supply (or placebo) will be obtained at an outpatient pharmacy on or before day of surgery.

### 7.4.1 Dosage/Dosage Regimen

Topical Ophthalmic Antibiotic Ointment (e.g. poly-bacitracin, bacitracin). Apply a thin ribbon to surgical wounds 4 times a day (while awake) for 7 days.

OR

Artificial Tear Ointment. Apply a thin ribbon to surgical wounds 4 times a day (while awake) for 7 days.

### 7.4.2 Dispensing

Study drug or placebo will be dispensed by an outpatient pharmacist.

### 7.4.3 Administration Instructions

See 7.4.1

## 7.5 Supply of Study Drug at the Site

n/a

### 7.5.1 Storage

n/a

## 7.6 Study Drug Accountability

n/a

## 7.7 Measures of Treatment Compliance

Subjects will be asked to keep a patient diary noting the day and date they take their study drug and any adverse events. They will be asked to bring their patient diary to each study visit along with all used and unused study drug containers.

## 8.1 Clinical Assessments

### 8.1.1 Concomitant Medications

All concomitant medication and concurrent therapies will be documented at Visit 1 and 2 and at early termination when applicable. Dose, route, unit frequency of administration, and indication for administration and dates of medication will be captured.

### 8.1.2 Demographics

Demographic information (date of birth, gender, race) will be recorded at Visit 1.

### 8.1.3 Medical History

Relevant medical history, including history of current disease, other pertinent respiratory history, and information regarding underlying diseases will be recorded at Visit 1.

### 8.1.4 Physical Examination

A complete eye examination will be performed by either the investigator or a subinvestigator who is a physician at Visit 1. New abnormal eye exam findings must be documented and will be followed by a physician or other qualified staff at the next scheduled visit.

### 8.1.5 Adverse Events

Information regarding occurrence of adverse events will be captured throughout the study. Duration (start and stop dates and times), severity/grade, outcome, treatment and relation to study drug will be recorded on the case report form (CRF).

## 9.2 Visit 2 (Post-operative week 1)

1. Record any Adverse Experiences and/or Review subject diary for adverse experiences and dosing compliance.
2. Concomitant medications review.
3. Perform abbreviated eye examination.
4. Determine presence or absence of surgical site infection.
5. Determine presence or absence of drug/placebo allergies.
6. Determine if patient is immunocompromised.
7. Start treatment if infection present.
8. Document findings using Apex smartphase, “.RKRVEYELIDPOST”

## 9.3 Visit 3 (Only if surgical site infection present at Visit 2.)

1. Record any Adverse Experiences and/or Review subject diary for adverse experiences and dosing compliance.
2. Record changes to concomitant medications.
3. Perform abbreviated eye examination.
4. Note duration of treatment and if infection resolved.

## 9.4 Early Withdrawal Visit

1. Record any Adverse Experiences and/or Review subject diary for adverse experiences and exclusionary medication use.
2. Record changes to concomitant medications.
3. Perform complete eye examination.

# 10 ADVERSE EXPERIENCE REPORTING AND DOCUMENTATION

## 10.1 Adverse Events

An adverse event (AE) is any untoward medical occurrence in a clinical investigation of a patient administered a pharmaceutical product and that does not necessarily have a causal relationship with the treatment. An AE is therefore any unfavorable and unintended sign (including an abnormal laboratory finding), symptom or disease temporally associated with the administration of an investigational product, whether or not related to that investigational product. An unexpected AE is one of a type not identified in nature, severity, or frequency in the current Investigator's Brochure or of greater severity or frequency than expected based on the information in the Investigator's Brochure.

The Investigator will probe, via discussion with the subject, for the occurrence of AEs during each subject visit and record the information in the site's source documents. Adverse events will be recorded in the patient CRF. Adverse events

will be described by duration (start and stop dates and times), severity, outcome, treatment and relation to study drug, or if unrelated, the cause.

### AE Severity

The National Cancer Institute's Common Terminology Criteria for Adverse Events (CTCAE) Version 3.0 should be used to assess and grade AE severity, including laboratory abnormalities judged to be clinically significant. The modified criteria can be found in the study manual. If the experience is not covered in the modified criteria, the guidelines shown in Table 1 below should be used to grade severity. It should be pointed out that the term "severe" is a measure of intensity and that a severe AE is not necessarily serious.

**Table 1. AE Severity Grading**

Severity (Toxicity Grade)	Description
Mild (1)	Transient or mild discomfort; no limitation in activity; no medical intervention or therapy required. The subject may be aware of the sign or symptom but tolerates it reasonably well.
Moderate (2)	Mild to moderate limitation in activity, no or minimal medical intervention/therapy required.
Severe (3)	Marked limitation in activity, medical intervention/therapy required, hospitalizations possible.
Life-threatening (4)	The subject is at risk of death due to the adverse experience as it occurred. This does not refer to an experience that hypothetically might have caused death if it were more severe.

### AE Relationship to Study Drug

The relationship of an AE to the study drug should be assessed using the following the guidelines in Table 2.

**Table 2. AE Relationship to Study Drug**

Relationship to Drug	Comment
Definitely	Previously known toxicity of agent; or an event that follows a reasonable temporal sequence from administration of the drug; that follows a known or expected response pattern to the suspected drug; that is confirmed by stopping or reducing the dosage of the drug; and that is not explained by any other reasonable hypothesis.

Probably	An event that follows a reasonable temporal sequence from administration of the drug; that follows a known or expected response pattern to the suspected drug; that is confirmed by stopping or reducing the dosage of the drug; and that is unlikely to be explained by the known characteristics of the subject's clinical state or by other interventions.
Possibly	An event that follows a reasonable temporal sequence from administration of the drug; that follows a known or expected response pattern to that suspected drug; but that could readily have been produced by a number of other factors.
Unrelated	An event that can be determined with certainty to have no relationship to the study drug.

## 10.2 Serious Adverse Experiences (SAE)

An SAE is defined as any AE occurring at any dose that results in any of the following outcomes:

- death
- a life-threatening adverse experience
- inpatient hospitalization or prolongation of existing hospitalization
- a persistent or significant disability/incapacity
- a congenital anomaly/birth defect

Other important medical events may also be considered an SAE when, based on appropriate medical judgment, they jeopardize the subject or require intervention to prevent one of the outcomes listed.

### 10.2.1 Serious Adverse Experience Reporting

Study sites will document all SAEs that occur (whether or not related to study drug) per [UCSF CHR Guidelines](#). The collection period for all SAEs will begin after informed consent is obtained and end after procedures for the final study visit have been completed.

In accordance with the standard operating procedures and policies of the local Institutional Review Board (IRB)/Independent Ethics Committee (IEC), the site investigator will report SAEs to the IRB/IEC.

## 10.3 Medical Monitoring

The DSMC will receive regular updates, including information such as: number of patients screened, number of participants enrolled, number of participants randomized/receiving treatment, number of participants lost to follow-up, number of participants meeting the outcome definition, and number of participants with an adverse event. These updates will be made after each consecutive set of 25

participants has been enrolled. As part of this regular review process, the DSMC will make a determination at each review whether the study can continue.

[name] should be contacted directly at these numbers to report medical concerns or questions regarding safety.

[contact]

## **11 DISCONTINUATION AND REPLACEMENT OF SUBJECTS**

### **11.1 Early Discontinuation of Study Drug**

A subject may be discontinued from study treatment at any time if the subject, the investigator, or the Sponsor feels that it is not in the subject's best interest to continue. The following is a list of possible reasons for study treatment discontinuation:

- Subject withdrawal of consent (or assent)
- Subject is not compliant with study procedures
- Adverse event that in the opinion of the investigator would be in the best interest of the subject to discontinue study treatment
- Protocol violation requiring discontinuation of study treatment
- Lost to follow-up
- Sponsor request for early termination of study

If a subject is withdrawn from treatment due to an adverse event, the subject will be followed and treated by the Investigator until the abnormal parameter or symptom has resolved or stabilized.

All subjects who discontinue study treatment should come in for an early discontinuation visit as soon as possible and then should be encouraged to complete all remaining scheduled visits and procedures.

All subjects are free to withdraw from participation at any time, for any reason, specified or unspecified, and without prejudice.

Reasonable attempts will be made by the investigator to provide a reason for subject withdrawals. The reason for the subject's withdrawal from the study will be specified in the subject's source documents Refer to Section 9.4 for early termination procedures.

